5.9.2 Clinical Events Committee (CEC)

An independent CEC will be responsible for providing review and adjudication of pre-defined clinical events, including major and minor complications, deaths, or other events or endpoints as outlined in the CEC Charter. The CEC is responsible for reviewing all reportable Adverse Events as defined in section 8.2.

The CEC will also advise the Sponsor regarding the continuing safety of subjects and those yet to be recruited, as well as the continuing validity and scientific merit of the clinical investigation. CEC members will not be investigators in the clinical investigation. At any time during the investigation, the CEC may offer opinions or provide formal recommendations concerning aspects of the study that impact subject safety (e.g. safety-related protocol changes or input regarding study-related adverse event rates).

The primary function, responsibilities and membership of the CEC will be described in detail in a CEC charter.

6 Statistical Considerations

The following section describes the statistical methods for the clinical investigation and justification of the design. For the Primary and Secondary Endpoints, pivotal IDE subjects will be analyzed separately from CAP subjects.

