8.2 Adverse Event Reporting

Safety surveillance within this trial (and the safety reporting performed by the investigator), starts as soon as the subject is enrolled. The safety surveillance and the safety reporting will continue until the last investigational visit has been performed, the subject is deceased, the subject/investigator concludes his/her participation into the clinical investigation or the subject withdrawal from the clinical investigation.

All adverse event data required to be reported will be collected throughout the clinical investigation and will be reported to the Sponsor on a CRF.

Adverse events will be monitored until they are adequately resolved or the subject has ended his/her participation in the trial, whichever comes first. The status of the subject's condition should be documented at each visit.

For the purposes of this clinical investigation the following events will be reported (see **Appendix B** for definitions):

- Unanticipated adverse device effects
- All adverse events viewed/interpreted by investigator to be potentially related to either a) the implant procedure or b) the study device (ADO II AS) regardless of seriousness

Note – If relatedness is unknown or cannot be determined, then the event must be reported.

Note – if a procedure is abandoned and a non-study device is used to close the PDA, adverse events associated with the non-study device will not be reported.

Records relating to the subject's subsequent medical course must be maintained and submitted (as applicable) to the Sponsor until the event has subsided or, in case of permanent impairment, until the event stabilizes and the overall clinical outcome has been ascertained. Adverse events will be monitored until they are adequately resolved. The status of the subject's condition should be documented at each visit.

SAE Reporting

Reportable adverse events that are deemed by the investigator to be serious should be reported to the Sponsor as soon as possible but no later than outlined below.

Clinical Site	Reporting timelines
All Sites	SAEs must be reported to the Sponsor no later than 3 calendar days from the day the site personnel became aware of the event or as per the investigative site's local requirements, if the requirement is more stringent than those outlined above.

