8.2.1 Subject Death

Subject deaths will be documented and reported to the Sponsor as soon as possible (but no later than 3 calendar days) after becoming aware of the event via the applicable CRF.

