Appendix B: Definitions

Non-study Specific Definitions

Adverse Event (AE)

Any untoward medical occurrence, unintended disease or injury, or untoward clinical signs (including abnormal laboratory findings) in subjects, users or other persons, whether or not related to the investigational medical device under clinical investigation.

This definition includes events related to the investigational medical device (ADO II AS) as well as events related to the procedures involved in the clinical protocol.

Serious Adverse Event (SAE)

An adverse event that led to:

- Death
- A serious deterioration in the health of the subject, that either resulted in:
 - A life-threatening illness or injury OR
 - A permanent impairment to a body structure or a body function OR
 - An in-patient or prolonged hospitalization OR
 - A medical or surgical intervention to prevent life-threatening illness or injury or permanent impairment to a body structure or a body function OR
 - A malignant tumor
- Fetal distress, fetal death or a congenital abnormality or birth defect
- A planned hospitalization for a pre-existing condition, or a procedure required by the CIP is not considered a serious adverse event.

Adverse Device Effect (ADE)

An adverse event related to the use of an investigational medical device.

This definition includes adverse events resulting from insufficient or inadequate instructions for use, deployment, implantation, installation, or operation, or any malfunction of the investigational medical device.

This definition includes any event resulting from the use error or from intentional misuse of the investigational medical device.

Serious Adverse Device Effect (SADE)

Adverse device effect that has resulted in any of the consequences characteristic of a serious adverse event.

Unanticipated Adverse Device Effect (UADE)

As defined in 21 CFR §812.3, unanticipated adverse device effects (UADE) are defined as any serious adverse effect on health or safety or any life-threatening problem or death caused by, or associated with, a device, if that effect, problem, or death was not previously identified in nature, severity, or degree of incidence in the CIP or application (including a supplementary plan or application), or any other unanticipated serious problem associated with a device that relates to the rights, safety, or welfare of subjects.

Study Specific Definitions

Related:

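### A non-fatal severe event that the investigator affirmatively calls unrelated is not reportable under 8.2 and, on the visible text, has no stated route to the CEC, so the plan states no way to correct a wrong call in the primary safety endpoint

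*Combined protocol and SAP*

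**What the plan says.** **Endpoint.** Section 6.1.1 takes the proportion of subjects with a major complication in the 180 days after an implant attempt. Appendix B limits major complications to events related to the device or procedure. They must also be fatal, be life-threatening, leave lasting or significant disability, or need major open surgery under general anesthesia.

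**What is reported.** Section 8.2 lists two classes. One is unanticipated adverse device effects (UADEs). The other is "All adverse events viewed/interpreted by investigator to be potentially related to either a) the implant procedure or b) the study device (ADO II AS"), whatever their seriousness. A note adds: "If relatedness is unknown or cannot be determined, then the event must be reported". Section 8.2.1 adds deaths with no condition on relatedness: "Subject deaths will be documented and reported to the Sponsor as soon as possible". Case report form collection follows the same limit: "All adverse event data required to be reported will be collected throughout the clinical investigation".

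**Serious events.** The lead-in to the SAE rule reads: "Reportable adverse events that are deemed by the investigator to be serious should be reported to the Sponsor as soon as possible". The timing table beneath it requires SAEs to go to the sponsor within 3 calendar days, and does not repeat the restriction to reportable events.

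**Adjudication.** Section 5.9.2 says: "The CEC is responsible for reviewing all reportable Adverse Events as defined in section 8.2". It also gives the CEC pre-defined events, "including major and minor complications, deaths, or other events or endpoints as outlined in the CEC Charter". The Charter is not among the documents.

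**The concern.** Relatedness is part of the endpoint definition, so whoever decides relatedness decides whether a severe event counts. For most events the CEC can revise the investigator's view. For one class the investigator's view also decides whether the CEC sees the event at all.

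The trial is single-arm, so the absolute complication rate is itself the safety result and no control rate is exposed to the same error. The error also runs one way: the CEC can remove a reported event from the count, but it cannot add one that it never receives.

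Perforation, tamponade and device embolization are plainly procedural and unlikely to be called unrelated. The exposed events are those that the underlying condition could also produce. Section 2.1 associates a significant PDA in premature infants with pulmonary hemorrhage, intraventricular hemorrhage and necrotizing enterocolitis. Section 4.5.2 admits infants from 700 g. Appendix B lists persistent or worsening respiratory instability as an example of a major complication.

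**Working it through.** **Step 1: trace each class of severe event.**

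| Severe event | Reportable? | Stated route to the CEC? |
|---|---|---|
| Fatal, any attribution | Yes (8.2.1) | Yes (5.9.2 names deaths) |
| Non-fatal, viewed as potentially related | Yes (8.2) | Yes |
| Non-fatal, relatedness unknown | Yes (note in 8.2) | Yes |
| Non-fatal, affirmatively called unrelated | No, unless the SAE table is read apart from its lead-in | None |

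**Step 2: look for another way in for the last row.**
- UADE: Appendix B requires a link to the device, as in "any life-threatening problem or death caused by, or associated with, a device". An event called unrelated to the device does not meet that.
- Seriousness: the SAE lead-in covers only events that are already reportable.
- CEC review of major complications: an event called unrelated does not meet the definition, so it would not be presented as one.
- Monitoring (section 10), audits (11.2) and complaints involving an adverse event (8.2.3): each could bring an event to light. None is stated to send it to the CEC.
- Echo core lab (5.8): it reads the TTEs, not clinical events.

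**Step 3: illustrate the size.** The visible text gives no expected rate or success criterion, so there is no stated figure to reproduce. The sample sizes are from 4.1: 40 subjects for the PMA submission, 25 subjects above 2 kg for the alternative submission, and a minimum of 15 subjects at 2 kg or less. The event counts are assumed. The interval is the exact binomial 95% interval named in 6.1.1.1.

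With 0 events in n, the upper limit is U = 1 − 0.025^(1/n). With 1 event, U solves (1 − U)^n + nU(1 − U)^(n−1) = 0.025.

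| n | 0 counted: rate (upper limit) | 1 counted: rate (upper limit) |
|---|---|---|
| 40 | 0% (8.8%) | 1/40 = 2.5% (13.2%) |
| 25 | 0% (13.7%) | 1/25 = 4.0% (20.4%) |
| 15 | 0% (21.8%) | 1/15 = 6.7% (31.9%) |

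For n = 40 with no events, U = 1 − 0.025^(1/40) = 8.8%. For n = 40 with one event, U = 13.2% solves the second equation.

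These figures show what one event is worth at these sample sizes. Any missed event, from any cause, would give the same numbers, so they are not evidence that an event would be missed.

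**The case against.** **The exposed class is narrow.** The threshold in 8.2 is potential relatedness, which is lower than the four-criterion Appendix B test of related. Where the cause is truly uncertain, the note in 8.2 requires a report. What remains is a confident exclusion of relatedness that is wrong. This stands, and the point is limited to that class.

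**A reader might infer that a wrong call can never be corrected.** The documents do not support that. Monitors review source records, the sponsor may audit with direct source access, and a complaint involving an adverse event requires a form. Any of these could lead to a query. They are indirect checks, however, and none is stated to lead to adjudication. What can be said is that the plan states no mechanism for correction.

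**A wider trigger may exist out of sight.** The Charter may name further events, and text is redacted after the primary safety endpoint, after its analysis method and after the complication definitions. This stands as a condition on the conclusion. Even if the Charter is wider, the visible 8.2 would still not require sites to report the events that the Charter needs.

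**The SAE table may already cover these events.** Read alone, it covers all SAEs, and Appendix B builds the SAE definition on adverse events of any relatedness. The lead-in probably governs, but the text can be read both ways. That weakens a flat statement that the events are excluded, and it is itself a reason to clarify 8.2.

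**Limiting collection to potentially related events is a legitimate choice in sick neonates.** It limits the reporting burden, and wider collection has a real cost. This stands as a cost to be weighed. It does not supply independent review of an attribution that decides the primary endpoint.

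**Conclusion.** The point holds in a limited form. On the visible text, a non-fatal event that meets an Appendix B severity criterion, and that the investigator affirmatively calls unrelated, is not reportable under 8.2 and has no stated route to the CEC. The plan states no mechanism for correcting a wrong call of this kind. Deaths, potentially related events and events of unknown relatedness are not affected.

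The conclusion assumes that the SAE lead-in governs its table, and that neither the Charter nor the redacted text contains a wider trigger.

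The direction of any error is certain: it can only lower the rate. Its size is not known. One event is worth 2.5 percentage points at n = 40, but the documents give no misattribution rate and do not show that the reported rate would change. A reader might infer that the safety conclusion would be reversed. No success criterion is visible, so the documents do not support that inference.

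**What to change.** - In 8.2 and 5.9.2, require every non-fatal event through 180 days that is life-threatening, leaves lasting or significant disability, or needs major open surgery under general anesthesia to be reported and sent to the CEC, whatever the investigator's attribution. The CEC decides relatedness.
- For subjects without a successful implant, whom section 5 withdraws after the 30-day visit, apply the rule through study exit. State how it fits with the note in 8.2 on events associated with a non-study device.
- Make the SAE lead-in and its table say the same thing.
- Align the Charter if needed. If it already has this trigger, bring 8.2 into line with it.
- Deaths need no change, because 8.2.1 and 5.9.2 already cover them.

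**Cost.** There will be additional adverse event forms and CEC cases from background neonatal intensive care morbidity, in a number that the documents do not allow to be estimated. Limiting the rule to the Appendix B severity criteria avoids collecting every background event. The safety rate may turn out less favorable. The change uses the existing committee and adds no visits or procedures.

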8.2.1 Subject Death

Subject deaths will be documented and reported to the Sponsor as soon as possible (but no later than 3 calendar days) after becoming aware of the event via the applicable CRF.

8.2.2 Unanticipated Adverse Device Effect

If an unanticipated adverse device effect occurs, the investigator must notify the Sponsor and the IRB immediately, but no later than 3 calendar days of the investigator's knowledge of the event, as required by 21 CFR §812.150. St. Jude Medical will take any steps necessary to investigate the event, and, as appropriate, will be responsible for notifying FDA and all other participating IRBs and investigators.

8.2.3 Complaints

During the study, the investigator will be responsible for reporting all complaints. If the complaint does not involve an AE, the investigator must notify the St. Jude Medical (SJM) Postmarket Surveillance Department by emailing the information on the device to [contact] or calling [contact] as soon as possible after becoming aware of the complaint.

If the complaint involves an AE, the investigator must complete an AE Case Report Form (CRF) including the information on the complaint and report to St Jude Medical as soon as possible.

Should a subject death be caused by the SJM device or the device contributed to the death, the investigator should complete a Form 3500A (MedWatch) and submit to SJM and the FDA within 10 days after becoming aware of the event.

8.3 Source records

Source documents will be created and maintained by the investigational site team throughout the clinical investigation. The data reported on the CRFs will be derived from, and be consistent with, these source documents, and any discrepancies will be explained in writing.

8.4 Records retention

The Sponsor and the Principal Investigators will maintain the clinical investigation documents as required. Measures will be taken to prevent accidental or premature destruction of these documents. The Principal Investigator or the Sponsor may transfer custody of records to another person/party and document the transfer at the investigational site or the Sponsor's facility, as appropriate.

These documents must be retained by the investigational site for a period of 2 years after the conclusion of the clinical investigation and made available for monitoring or auditing by the Sponsor's representative or representatives of the applicable regulatory agencies.

All original source documents must be stored for the maximum time required by the regulations at the hospital, research institute, or practice in question. If original source documents can no longer be maintained at the site, the investigator will notify the Sponsor.

9 Clinical Data Handling

The Sponsor will be responsible for the data handling. The Sponsor and/or its affiliates will be responsible for compiling and submitting all required reports to governmental agencies. Data will be analyzed by the Sponsor

and may be transferred to the Sponsor's locations worldwide and/or any other worldwide regulatory authority in support of a market-approval application.

9.1 Protection of Personally Identifiable Information

St. Jude Medical respects and protects personally identifiable information collected or maintained for this clinical investigation. The privacy of each subject and confidentiality of his/her information will be preserved in reports and when publishing any data. Confidentiality of data will be observed by all parties involved at all times throughout the clinical investigation. All data will be secured against unauthorized access.

9.2 Data Management Plan

A Data Management Plan (DMP) will describe procedures used for data review, database cleaning, and issuing and resolving data queries. If appropriate, the DMP may be updated throughout the clinical investigation duration. All revisions will be tracked and document controlled.

Subject data will be captured in a validated electronic data capture (EDC) system hosted by the Sponsor.

Only authorized site personnel will be permitted to enter the CRF data through the EDC system deployed by St. Jude Medical. An electronic audit trail will be used to track any subsequent changes of the entered data.

9.3 Document and Data Control

9.3.1 Traceability of Documents and Data

The investigator will ensure accuracy, completeness legibility and timeliness of the data reported to the Sponsor on the CRFs and in all required reports.

9.3.2 Recording Data

The CRF will be reviewed by the authorized site personnel. An appropriate comment will be provided to explain changes to data reported on the CRF.

10 Monitoring

It is the responsibility of the Sponsor to ensure the clinical investigation is conducted, recorded and reported according to the approved CIP, subsequent amendment(s), applicable regulations and guidance documents.

Monitoring will be conducted according to St. Jude Medical's Clinical Monitoring work instruction. Prior to beginning the clinical investigation, the Sponsor will contact the investigator or designee to discuss the clinical investigation and data requirements. A designated monitor will periodically review the subject records and associated source documents. The investigator shall make subject and clinical investigation records available to the clinical monitor for monitoring.

11 Compliance Statement

11.1 Statement of Compliance

In addition to applicable regional or local laws and regulations, this clinical investigation will be conducted in compliance with the most current version of the World Medical Association (WMA) Declaration of Helsinki

and 21 CFR Parts 50, 54, 56 and 812. In the event of any conflicts, local laws and regulations will have precedence and in such cases, good faith efforts will be made to adhere to the intent of the other documents.

The investigator will sign a Clinical Trial Agreement and agrees to be compliant with it. The investigator will not start enrolling subjects or requesting informed consent from any subject prior to obtaining IRB approval and relevant Regulatory Authority approval, if applicable, and authorization from the Sponsor in writing for the clinical investigation. If additional requirements are imposed by the IRB or relevant Regulatory Authority, those requirements will be followed. If any action is taken by an IRB or a relevant Regulatory Authority with respect to the clinical investigation, that information will be forwarded to the Sponsor.

11.2 Quality Assurance audits and Regulatory Inspections

The investigator and/or delegate should contact the Sponsor immediately upon notification of a regulatory authority inspection at the site. A monitor or designee will assist the investigator and/or delegate in preparing for the audit. The Sponsor may perform quality assurance audits, as required.

The Principal Investigator or institution will provide direct access to source data during and after the clinical investigation for monitoring, audits, IRB review and regulatory authority inspections, as required. The Principal Investigator or institution will obtain permission for direct access to source documents from the subject, hospital administration and national regulatory authorities before starting the clinical investigation.

11.3 Repeated and Serious Non-Compliance

In the event of repeated non-compliance or a one-time serious non-compliance, as determined by the Sponsor, a monitor or designee will attempt to secure compliance by one or more of the following actions:

- Visiting the investigator,
- Contacting the investigator by telephone,
- Contacting the investigator in writing,
- Retraining of the investigator.

If an investigator is found to be repeatedly non-compliant with the signed agreement, the CIP or any other conditions of the clinical investigation, the Sponsor will either secure compliance or, at its sole discretion, terminate the investigator's participation in the clinical investigation. In case of termination, the Sponsor will inform the responsible regulatory authority, as required, and ensure that the IRB is notified, either by the Principal Investigator or by the Sponsor.

12 Suspension or premature termination of the clinical investigation

The Sponsor reserves the right to terminate the clinical investigation at any stage, with appropriate written notice to the investigators, IRB and relevant Regulatory authorities, if required.

A Principal Investigator, IRB or regulatory authority may suspend or prematurely terminate participation in a clinical investigation at the investigational sites for which they are responsible. The investigators will follow the requirements specified in the Clinical Trial Agreement.

If suspicion of an unacceptable risk to subjects arises during the clinical investigation or when so instructed by the IRB or regulatory authority, the Sponsor may suspend the clinical investigation while the risk is assessed. The Sponsor will terminate the clinical investigation if an unacceptable risk is confirmed. If the Sponsor completes an analysis of the reasons for the suspension, implements the necessary corrective

actions, and decides to lift the temporary suspension, the Sponsor will inform the Principal Investigators, IRB, or regulatory authority, where appropriate, of the rationale, providing them with the relevant data supporting this decision. Approval from the IRB or regulatory authority, where appropriate, will be obtained before the clinical investigation resumes. If subjects have been informed of the suspension, the Principal Investigator or authorized designee will inform them of the reasons for resumption.

If the Sponsor suspends or prematurely terminates the clinical investigation at an individual investigational site in the interest of safety, the Sponsor will inform all other Principal Investigators.

If suspension or premature termination occurs, the Sponsor will remain responsible for providing resources to fulfill the obligations from the CIP and existing agreements for following up the subjects enrolled in the clinical investigation, and the Principal Investigator or authorized designee will promptly inform the enrolled subjects at his/her investigational site, if appropriate.

13 Clinical Investigation Conclusion

The clinical investigation will be concluded when:

- All sites are closed AND
- The final report has been provided to investigators or the Sponsor has provided formal documentation of clinical investigation closure.

14 Publication Policy

Publications or presentations of clinical investigation methods or results will adhere to St. Jude Medical's publication policy, which is based on Good Publication Practices and International Committee of Medical Journal Editors (ICMJE) guidelines. A copy of the policy will be provided upon request of the investigator.

Publication planning and authorship determinations will be overseen by the Publications Committee (see section 5.10.1), and investigators will be notified via email about the dissemination of study data and opportunities for involvement as authors on publications/presentations.

15 Reporting Results on ClinicalTrials.gov Website

Upon receiving IDE approval from the FDA, this clinical investigation will be registered on ClinicalTrials.gov. A full report of the pre-specified outcomes, regardless of the results, will be made public through the ClinicalTrials.gov website no later than 12 months after clinical investigation completion, as required by section 801 of the FDA Amendments Act. If this clinical investigation is terminated early, the Sponsor will make every effort to hasten the release of the pre-specified outcomes through the ClinicalTrials.gov website.

[REDACTED]

[REDACTED]

[REDACTED]

[REDACTED]

[REDACTED]

[REDACTED]

[REDACTED]

[REDACTED]

[REDACTED]	[REDACTED]	[REDACTED]	[REDACTED]	[REDACTED]
[REDACTED]	[REDACTED]	[REDACTED]	[REDACTED]	[REDACTED]
[REDACTED]	[REDACTED]	[REDACTED]	[REDACTED]	[REDACTED]
[REDACTED]	[REDACTED]	[REDACTED]	[REDACTED]	[REDACTED]

[REDACTED]

[REDACTED]	[REDACTED]	[REDACTED]	[REDACTED]	[REDACTED]
			[REDACTED]	[REDACTED]
[REDACTED]	[REDACTED]	[REDACTED]	[REDACTED]	[REDACTED]

